10.4. Sample Collection and Testing

[Attachment 1](#) lists the schedule for sample collections in this study.

[Attachment 2](#) lists the specific tests that will be performed for this study and whether these will be performed at a central or local laboratory.

[Attachment 6](#) provides a summary of the estimated maximum number and volume of invasive samples, for all sampling, during the study.

[Attachment 7](#) lists the schedule for PK sampling during the study.

10.4.1. Samples for Study Qualification and Health Monitoring

Blood samples will be collected to determine whether patients meet inclusion/exclusion criteria and to monitor patient health. Central hematology and chemistry labs may be drawn up to 3 days prior to Day 1 of each cycle. Enrollment and treatment decisions may be based upon results of tests performed locally. If local laboratory tests are used for this purpose, then a duplicate specimen must be submitted to the central laboratory. Discrepancies between local and central

laboratory that may have an impact on eligibility or treatment decisions will not be considered protocol deviations.

Investigators must document their review of each laboratory safety report.

Samples collected for specified laboratory tests will be destroyed within 60 days of receipt of confirmed test results. Tests are run and confirmed promptly whenever scientifically appropriate. When scientific circumstances warrant, however, it is acceptable to retain samples to batch the tests run, or to retain the samples until the end of the study to confirm that the results are valid. Certain samples may be retained for a longer period, if necessary, to comply with applicable laws, regulations, or laboratory certification standards.

10.4.2. Samples for Tailoring Biomarkers

There is growing evidence that genetic variation may impact a patient's response to therapy. Variable response to therapy may be due to genetic determinants that impact drug absorption, distribution, metabolism, and excretion, the mechanism of action of the drug, the disease etiology and/or the molecular subtype of the disease being treated. Therefore, where local regulations and ERBs allow, a blood sample will be collected for pharmacogenetic analysis.

Samples for biomarker research to be collected from all patients in this study:

- blood
- tumor tissue

Analyses may include, but are not limited to, nucleic acid and protein profiles to better understand the disease process and to develop predictive biomarkers.

These samples are described in the following sections.

10.4.2.1. Archived Tumor Tissue

For patients in the study, a small amount of preserved tumor tissue, previously taken to evaluate the patient's disease, should be requested for biomarker research.

Formalin-fixed paraffin-embedded tumor tissue should be in a whole block, partial block, or unstained slides. Any whole block submitted will be returned to the site. Any partial blocks or slides will either be returned or discarded within 15 years after last patient visit for the trial.

In tumor tissue samples, the CDK4/6 pathway components (for example, Rb) and markers relevant breast cancer pathogenesis may be evaluated to assess any potential correlation with response to abemaciclib. Tumor samples may be analyzed to explore potential tumor gene signature(s) associated with response or resistance to abemaciclib therapy. These studies may be analyzed at a laboratory designated by the sponsor and may include IHC of proteins, FISH for copy number amplifications, RNA gene-expression profiling, and/or genetic analyses of the tumor specimen DNA. Such analyses may employ targeted or high-throughput sequencing approaches. For this purpose, the results of this analysis will be correlated with clinical efficacy data.

10.4.2.2. Blood Samples for Pharmacogenetic Evaluations

Where local regulations and ERBs allow, a blood sample will be collected for pharmacogenetic analysis. Samples may be genotyped and analysis may be performed to evaluate a genetic association with response to abemaciclib. These investigations may be limited to a focused candidate gene study or, if appropriate, genome-wide analysis may be performed to identify regions of the genome associated with the variability observed in drug response. The pharmacogenetic biomarker samples will only be used for investigations related to disease and drug or class of drugs under study in the context of this clinical program. They will not be used for broad exploratory unspecified disease or population genetic analysis.

The samples will be coded with the patient number and stored for up to a maximum 15 years after the last patient visit for the study at a facility selected by the sponsor. The samples and any data generated from them can only be linked back to the patient by investigator site personnel. The duration allows the sponsor to respond to regulatory requests related to the study drug.

Samples will be destroyed according to a process consistent with local regulation.

10.4.2.3. Plasma Samples for Exploratory Biomarker Evaluations

Plasma samples will be collected and analysis may be performed on biomarkers that may play a role in the abemaciclib mechanism of action (refer to [Attachment 1](#)). The evaluation of these samples may involve analysis of DNA, RNA, and proteins (including any of these components derived from exosomes) to investigate their association with observed clinical outcomes to study drug. The samples will be coded with the patient number and stored for up to a maximum 15 years. Details for collecting, processing, and storing the samples are similar those provided in Section [10.4.2.2](#).

10.4.3. Samples for Drug Concentration Measurements ***Pharmacokinetics***

At the visits and times specified in the Pharmacokinetic Sampling Schedule ([Attachment 7](#)), venous blood samples of approximately 4 mL each will be collected to determine the plasma concentrations of abemaciclib and its metabolites LSN2839567, LSN3106726, and LSN3106729, as well as plasma concentrations of fulvestrant.

Separate blood samples are not required for the parent, its metabolites, and fulvestrant. After obtaining plasma, samples will be aliquoted into 2 approximately equal portions by site personnel, one for the determination of plasma concentrations of abemaciclib and its metabolites and the other for the determination of plasma concentrations of fulvestrant. Instructions for the collection and handling of blood samples will be provided by the sponsor. It is preferred that the blood samples be obtained from a peripheral location. Blood samples will be allowed from central access devices, but a sample drawn from a central catheter of any type for PK must take precautions to prevent obtaining a dilute sample. If multiple samples are obtained centrally, the PK sample should be the last specimen drawn to reduce the potential for a diluted or improperly drawn sample. The actual date and time (24-hour clock time) of each sampling will be recorded. A maximum of 5 samples may be drawn at additional time points during the study if warranted and agreed upon between both the investigator and Lilly.

These samples will be analyzed at a laboratory designated by the sponsor. Plasma concentrations of abemaciclib plus its metabolites LSN2839567, LSN3106726, and LSN3106729 will be assayed using a validated liquid chromatography/tandem mass spectrometry (LC/MS/MS) method. Plasma concentrations of fulvestrant will also be analyzed using a validated LC/MS/MS method. Bioanalytical samples collected to measure study drug concentration and metabolism and/or protein binding, will be retained for a maximum of 1 year following last patient visit for the study. The PK samples will be stored at a facility designated by the sponsor.

Drug concentration information that may unblind the study will not be reported to investigative sites or blinded personnel until the study has been unblinded.

10.5. Appropriateness of Measurements

Efficacy measurements by radiographic imaging are standard, widely used, and generally recognized as reliable, accurate, and able to discriminate between effective and ineffective agents.

Safety measurements by laboratory monitoring are standard, widely used, and generally recognized as reliable, accurate, and able to discriminate between agents with acceptable and unacceptable safety profiles.

11. Data Quality Assurance

To ensure accurate, complete, and reliable data, Lilly or its representatives will do the following:

- provide instructional material to the study sites, as appropriate
- sponsor start-up training to instruct the investigators and study coordinators. This session will give instruction on the protocol, the completion of the eCRFs, and study procedures.
- make periodic visits to the study site
- be available for consultation and stay in contact with the study site personnel by mail, telephone, and/or fax
- review and evaluate eCRF data and use standard computer edits to detect errors in data collection
- conduct a quality review of the database

In addition, Lilly or its representatives will periodically check a sample of the patient data recorded against source documents at the study site. The study may be audited by Lilly or its representatives, and/or regulatory agencies at any time. Investigators will be given notice before an audit occurs.

To ensure the safety of participants in the study, and to ensure accurate, complete, and reliable data, the investigator will keep records of laboratory tests, clinical notes, and patient medical records in the patient files as original source documents for the study. If requested, the investigator will provide Lilly, applicable regulatory agencies, and applicable ERBs with direct access to original source documents.

11.1. Data Capture System

An electronic data capture system will be used in this trial. The site maintains a separate source for the data entered by the site into the sponsor-provided electronic data capture system.

Case report form data will be encoded and stored in a clinical trial database.

Any data for which the paper documentation provided by the patient will serve as the source document will be identified and documented by each site in that site's study file.

Bioanalytical data will be stored electronically in the bioanalytical laboratory's database. Data will subsequently be transferred from the bioanalytical laboratory to the Lilly generic labs system.

Data from complaint forms submitted to Lilly will be encoded and stored in the global product complaint management system.

12. Sample Size and Statistical Methods

12.1. Determination of Sample Size

The primary objective of this study is to compare abemaciclib plus fulvestrant versus placebo plus fulvestrant in terms of PFS for women with HR+, HER2- locally advanced or metastatic breast cancer.

This study will enroll 2 strata of patients according to prior endocrine therapy: endocrine therapy pretreated (EP) patients and endocrine therapy naïve (EN) patients.

The primary statistical analyses will be performed on patients in the EP stratum.

The initial study protocol specified an enrollment of 450 EP patients. Amendment (a) changed the starting dose of blinded study drug from 200 mg Q12H to 150 mg Q12H. In addition to describing the safety profile in the full EP safety population, safety analyses will be conducted in the subgroup of patients enrolled under Amendment (a) with a starting dose of 150 mg Q12H. In order to do this robustly, enrollment to the study will continue until 450 EP patients are enrolled at a starting dose of 150 mg Q12H. As of the implementation of Amendment (a), approximately 180 EP patients had been enrolled at a starting dose of 200 mg Q12H. Including these 180 patients, the final size of the EP stratum will be approximately $450 + 180 = 630$ patients.

Patients will be randomized in a 2:1 ratio using the following stratification factors: nature of disease (visceral metastases versus bone only metastases versus other) and sensitivity to endocrine therapy (primary resistance versus secondary resistance).

A 2-look group-sequential design of the primary endpoint will be used to accommodate an event-driven plan for the interim and final PFS analyses (see Section 12.2.7 for details). The final PFS analysis will be performed after 378 PFS events have occurred in the EP stratum (that is, a 40% censoring rate). Assuming a hazard ratio (HR) of 0.703, this sample size yields approximately 90% statistical power to detect superiority of the abemaciclib plus fulvestrant arm over the placebo plus fulvestrant arm with the use of a 1-sided log-rank test and a type I error of 0.025. If the true median PFS for the placebo plus fulvestrant arm is 6.5 months, then the HR of 0.703 amounts to an approximately 2.75-month (42%) improvement in median PFS for the abemaciclib plus fulvestrant arm under an additional assumption of exponential survival distribution.

OS is an important secondary endpoint for this study. OS will be tested only if the test of PFS is significant. The final OS analysis will be conducted at 441 OS events in the EP stratum (see Section 12.2.8 for details).

Prior to Amendment (b), no more than 100 patients were to be enrolled into the EN stratum. Amendment (b) removes the inclusion of EN patients and specifies that the previously enrolled EN patients will not be included in the primary analysis. It is anticipated that approximately 50 patients will be enrolled into this stratum.

12.2. Statistical and Analytical Plans

12.2.1. Analysis Populations

The ITT population will be comprised of all randomized patients randomized within the EP strata (either primary endocrine resistance or secondary endocrine resistance), per IWRS.

The safety population will include all randomized EP patients who receive at least one dose of any study drug.

Patients randomized within the ‘no prior endocrine therapy’ stratum comprise the EN population. Exploratory efficacy analyses will be performed on this population. The EN safety population will include all randomized EN patients who receive at least one dose of any study drug.

12.2.2. General Considerations

Statistical analysis of this study will be the responsibility of Lilly.

Primary statistical analyses will be conducted on the ITT population, as defined in Section 12.2.1. Analyses will be performed based on the treatment group to which patients were randomized (regardless of which treatment was received).

Safety analyses will be based on the Safety Population, as defined in Section 12.2.1. Patients will be grouped according to treatment received in Cycle 1.

Pharmacodynamic and/or tailoring biomarker analyses will be based on the subset of patients from the above populations from whom a valid assay result (according to laboratory guideline) has been obtained.

All tests of treatment effects will be conducted at a 2-sided alpha level of 0.05, unless otherwise stated. All tests of interactions will be conducted at a 2-sided alpha level of 0.1, and all confidence intervals (CIs) will be given at a 2-sided 95% level, unless otherwise stated.

Any change to the data analysis methods described in the protocol will require an amendment ONLY if it changes a principal feature of the protocol.

Before unblinding of the aggregate database, minor modifications or clarifications to the data analysis methods may be described and justified in the SAP.

Any other change to the data analysis methods described in the protocol, and the justification for making the change, will be described in the clinical study report.

The assumptions for each statistical method will be evaluated. If there is violation of assumptions, alternative statistical methods may be used.

Additional exploratory analyses of the data will be conducted as deemed appropriate.

12.2.3. Patient Disposition

A detailed description of patient disposition will be provided. It will include a summary of the number and percentage of patients entered into the study, enrolled in the study, and treated, as

well as number and percentage of patients completing the study or discontinuing (overall and by reason for discontinuation).

All patients entered in the study will be accounted for in the summation. The number of patients who do not qualify for analysis, who die, or who discontinue before treatment begins will be specified.

A summary of all important protocol deviations will be provided.

12.2.4. Patient Characteristics

Patient characteristics will include a summary, by treatment arm, of the following:

- patient demographics
- baseline disease characteristics
- preexisting conditions
- historical illnesses
- prior endocrine therapy
- prior chemotherapy (including both cytotoxic and targeted agents)

Other patient characteristics will be summarized as deemed appropriate.

12.2.5. Concomitant Therapy

Concomitant medication will be summarized by treatment arm in a frequency table listing the terms recorded on the eCRF.

12.2.5.1. Postdiscontinuation Therapy

The numbers and percentages of patients reporting postdiscontinuation therapies will be provided overall, by type of therapy (surgery, radiotherapy, or systemic therapy) and by drug name.

12.2.6. Treatment Compliance

The number of dose omissions, reductions, and delays, cycles received, and dose intensity will be summarized for all treated patients per treatment arm.

Treatment compliance information for blinded study drug will be collected through solid oral dosage unit counts at each tumor assessment visit. The estimate of percent compliance will be given by:

$$\text{Percent Compliance} = \frac{\text{Actual cumulative dose taken}}{\text{Expected cumulative dose to be taken}} \times 100$$

The actual cumulative dose taken will be determined based on counting the number of solid oral dosage units returned at each visit and subtracting that number from the number of dosage units dispensed. The expected cumulative dose to be taken will be determined based on the assigned dose and taking into account any dose reductions or omissions.

12.2.7. Primary Outcome and Methodology

The primary endpoint of this study is PFS. PFS time is measured from the date of randomization to the date of investigator-determined objective progression as defined by RECIST v1.1, or death from any cause. Patients who have neither progressed nor died will be censored at the day of their last radiographic tumor assessment (if available) or date of randomization if no post initiation (that is, postbaseline) radiographic assessment is available. The detailed censoring rules are described below (Table JPBL.12.1).

Table JPBL.12.1. Rules for Determining Date of Progression or Censor for Progression-Free Survival

Rule	Situation	Date of Progression or Censor	Outcome
1	No baseline tumor assessments	Date of Randomization	Censored
2	No post baseline assessments and no death	Date of Randomization	Censored
3	No documented progression and no death (with a post-baseline tumor assessment)	Date of last adequate tumor assessment	Censored
4	Patient lost to follow-up (or withdrew consent from study participation) before documented progression or death	Date of last adequate tumor assessment	Censored
5	Documented progression	Date of documented progression. If a tumor assessment was done on multiple days, use the earliest date for that visit.	Progressed
6	Death without documented progression	Date of death	Progressed
7	Documented progression or death after missing ≥ 2 consecutive post-baseline tumor assessments	Date of last adequate tumor assessment before missed assessments or date of randomization, whichever is later	Censored

Note: Progression-free survival and associated outcome is determined by the earliest of the dates above, if more than 1 situation applies.

The PFS analysis to test the superiority of abemaciclib to placebo in improving PFS time will be performed on the ITT population (as defined in Section 12.2.1) and will use the log-rank test stratified by nature of disease (visceral metastases versus bone only metastases versus other) and sensitivity to endocrine therapy (primary resistance versus secondary resistance). In addition, the Kaplan-Meier method (Kaplan and Meier 1958) will be used to estimate the PFS curves as well as PFS rates at every 3 months for each treatment group. These rates will be compared based on a normal approximation for the difference between the rates.

The 2-look group-sequential design of the primary endpoint will be used to accommodate an event-driven plan for the interim and final analyses. There is 1 planned interim analysis and 1 final analysis for PFS in this study. The interim analysis is planned to take place after

approximately 265 (approximately 70% of the planned) investigator-assessed PFS events have occurred. The cumulative 1-sided type I error rate of .025 will be maintained using the following method. At the interim analysis, the nominal significance level will be .00001. The remaining alpha will be spent at the final analysis. The resulting boundary p-value for the final analysis is dependent on the exact number of events observed at each analysis and can be calculated using the method of Slud and Wei (1982). If the analyses are performed at exactly 265 and 378 events, then the boundary p-value at the final analysis will be .02499996).

The actual boundary for the final analysis will be calculated based on the actual number of events observed at the time of each analysis using software that implements the α -spending scheme noted above (for example, ADDPLAN 6.0, SAS 9.2, or similar software).

If statistical significance is not observed at the interim analysis, the final PFS analysis will be performed after 378 PFS events have been observed in the ITT population based on investigator assessment. Once statistical significance is declared at the interim analysis or the final analysis, the study will be positive based on the primary endpoint of PFS, and testing of secondary endpoints will proceed as described in the SAP.

The interim PFS analyses will be performed by DMC. The requirements for unblinding the sponsor at the interim analyses are found in Section 12.2.15.

The primary test of PFS will compare the 2 treatment groups using a log-rank test stratified by the randomization factors.

A stratified Cox proportional hazard model (Cox 1972) with treatment as a factor will be used to estimate the HR and corresponding 95% CI with Wald's test p-value after adjusting for the same randomization variables specified for the primary analysis. An additional unstratified Cox regression model will be employed to explore the effects of prognostic variables, such as of the stratification variables and intrinsic/extrinsic factors, on treatment response.

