7.3. Discontinuations

7.3.1. *Discontinuation of Patients*

The criteria for enrollment must be followed explicitly. If the investigator site identifies a patient who did not meet enrollment criteria and who was inadvertently enrolled, the sponsor must be notified. If the sponsor identifies a patient who did not meet enrollment criteria and who was inadvertently enrolled, the investigator site will be notified. A discussion must occur between the sponsor CRP and the investigator to determine whether the patient may continue in the study, with or without study drug. Inadvertently enrolled patients may be maintained in the study and on study drug when the Lilly CRP agrees with the investigator that it is medically appropriate for that patient. The patient may not continue in the study with or without study drug if the Lilly CRP does not agree with the investigator's determination that it is medically appropriate for the patient to continue. The investigator must obtain documented approval from the Lilly CRP to allow the inadvertently enrolled patient to continue in the study with or without study drug.

In addition, patients will be discontinued from the study drug(s) and/or from the study in the following circumstances:

- Progressive disease (PD) as defined by RECIST v1.1.
- enrollment in any other clinical trial involving an investigational product or enrollment in any other type of medical research judged not to be scientifically or medically compatible with this study
- investigator decision
 - the investigator decides that the patient should be discontinued from the study or study drugs
 - if the patient, for any reason, requires treatment with another therapeutic agent that has been demonstrated to be effective for treatment of the study indication, discontinuation from the study drugs occurs prior to introduction of the new agent
- patient decision
 - the patient or the patient's designee (for example, parents or legal guardian) requests to be withdrawn from the study or study drug
- sponsor decision

- Lilly stops the study or stops the patient's participation in the study for medical, safety, regulatory, or other reasons consistent with applicable laws, regulations, and good clinical practice (GCP)

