10.1.3. Primary Efficacy Measure

The primary efficacy measure is progression-free survival as defined by RECIST Version 1.1 (Eisenhauer et al. 2009) provided in [Attachment 5](#).

Lilly or its designee will collect and store all tumor measurement images on all enrolled patients throughout the study. An independent review of imaging scans will be performed by an independent panel of radiologists.

The PFS time is measured from the date of randomization to the date of objective progression or the date of death due to any cause, whichever is earlier.

For those patients with nonmeasurable, bone only disease (refer to Inclusion Criterion [5]), objective progression will be established if at least 1 of the following criteria is met:

- the appearance of 1 or more new lesions (in bone or outside of bone), or
- unequivocal progression of existing bone lesions.

Pathologic fracture, new compression fracture, or complications of bone metastases will not be considered as evidence of disease progression, unless at least 1 of the above criteria is met.

For those patients with locally advanced disease for whom surgery is performed with no evidence of residual disease post-operatively, objective progression will be established if at least 1 of the following criteria is met:

- local recurrence, or
- new development of metastatic disease.

For those patients with locally advanced disease for whom surgery is performed with evidence of residual disease post-operatively, new baseline measurements should be taken and RECIST applied.

If a patient is not known to have progressed or died at the time of analysis, PFS time will be censored at the last known progression-free assessment. See Section 12.2.7 for detailed censoring rules.

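### PFS censoring Rule 1 has no death exception, so a death in a patient without a baseline tumor assessment is censored at randomization instead of counted as an event

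*Protocol*

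**What the plan says.** Protocol Section 12.2.7 defines PFS as the time from randomization to the "date of investigator-determined objective progression as defined by RECIST v1.1, or death from any cause". Section 10.1.3 agrees: "The PFS time is measured from the date of randomization to the date of objective progression or the date of death due to any cause". The running text of Section 12.2.7 restricts censoring to patients with no event: "Patients who have neither progressed nor died will be censored at the day of their last radiographic tumor assessment", or at randomization if there is no post-baseline radiographic assessment.

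Table JPBL.12.1 then gives seven rules. Those that matter here are:

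- Rule 1, "No baseline tumor assessments": date of randomization, censored.
- Rule 2, "No post baseline assessments and no death": date of randomization, censored.
- Rules 3 and 4 (no progression seen; lost to follow-up or consent withdrawn): each is limited to patients without a prior death.
- Rule 6, "Death without documented progression": date of death, counted as an event.
- Rule 7: progression or death after two or more consecutive missed post-baseline assessments is censored, at the later of randomization and the last adequate assessment before the gap.

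The note under the table settles overlaps: "Progression-free survival and associated outcome is determined by the earliest of the dates above, if more than 1 situation applies".

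The analysis set (Section 12.2.1) is every patient randomized in the endocrine-pretreated strata. A baseline scan is not a condition of membership.

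**The concern.** Of the four rules for absent data or follow-up, only Rule 1 lacks a death condition. Without a baseline assessment, RECIST progression may be impossible to judge, but a death can still be recognised and dated. The table nevertheless discards it.

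A patient censored at time zero is never at risk when an event occurs, so she contributes nothing to the log-rank test and is in effect removed from an intention-to-treat comparison. The same death counts for OS (Section 10.1.4) but not for PFS. The central-review PFS analysis in Section 12.2.9 uses the same table, so it would not reveal the loss.

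**Working it through.** **Rule logic.** Take a randomized endocrine-pretreated patient with no baseline assessment. Let day 0 be randomization and D the day of death.

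1. Rule 1 applies: day 0, censored.
2. If she dies without documented progression, Rule 6 also applies: day D, event.
3. The note takes the earlier date together with its outcome. Since D cannot precede day 0, Rule 1 prevails: time zero, censored.
4. The definition in Sections 10.1.3 and 12.2.7 gives time D, event. The two results disagree.

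**Which patients change if Rule 1 gains the death condition.** Scans are due on Days 1 to 7 of Cycles 3 and 5 (Section 10.1.1). With 28-day cycles and no delays, those windows open on Day 2 × 28 + 1 = 57 and Day 4 × 28 + 1 = 113.

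| Patient without a baseline assessment | As written | With the condition added |
|---|---|---|
| Alive at cutoff | Rule 1: day 0, censored | Unchanged |
| Dies without progression, before two consecutive post-baseline assessments are missed | Rule 1: day 0, censored | Rule 6: event at death |
| Never scanned, dies after the Cycle 3 and Cycle 5 assessments are both missed | Rule 1: day 0, censored | Rule 7: day 0, still censored |

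Only the second row changes. For a patient who is never scanned, that means deaths up to roughly the Cycle 5 window. For a patient scanned only after baseline, the result depends on what counts as an adequate assessment, which the supplied documents do not define.

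**The plan's power figure.** Inputs from Section 12.1: d = 378 events, hazard ratio 0.703, one-sided alpha 0.025, 2:1 allocation, power about 90%.

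- Formula (Schoenfeld): power = Φ( √(d × 2/3 × 1/3) × |ln HR| − 1.960 ).
- At 378: √84 = 9.165; × 0.3524 = 3.230; − 1.960 = 1.270; Φ = 0.898. The stated figure reproduces.
- At 372 (6 events lost): √82.67 = 9.092; × 0.3524 = 3.204; − 1.960 = 1.244; Φ = 0.893.

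**Range over an assumed number of lost events.** The documents give no count.

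| Events lost | Share of 630 | Power |
|---|---|---|
| 0 | 0% | 0.898 |
| 1 | 0.2% | 0.897 |
| 3 | 0.5% | 0.896 |
| 6 | 1.0% | 0.893 |
| 13 | 2.1% | 0.888 |

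These figures overstate the loss. The final analysis is triggered by 378 counted events, so uncounted deaths would mainly delay the cutoff.

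**The case against.** **The case is nearly excluded by design.** Inclusion criterion [2] requires radiologic evidence of progression, criterion [5] requires measurable or bone-only nonmeasurable disease, Section 10.1.1 requires baseline imaging for each patient, stratification needs the disease sites, and waivers are prohibited. This stands, and it is why the effect is small. Section 7.3.1 says that "Inadvertently enrolled patients may be maintained in the study and on study drug", but it requires sponsor agreement and does not mention missing scans. A reader might infer from it that such patients exist. It shows only that an ineligible patient can remain in follow-up.

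**The omission may be deliberate.** Rule 7 shows that the table does qualify the definition, so Rule 1 might be another intended exception. The documents do not settle this. But Rule 7 names death openly, whereas Rule 1 is silent and conflicts with the sentence that limits censoring to patients without an event. If an exception is meant, it should be stated.

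**No bias is shown.** Whether a baseline scan exists is essentially a pre-treatment characteristic, and the rule is identical in both arms. A reader might infer that the rule favors one arm; nothing in the documents supports that.

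**The main SAP was not supplied.** The SAP provided is an OS addendum that refers to JPBL SAP v4, and Sections 12.2.2 and 12.2.9 leave clarifications and sensitivity analyses to the SAP. These deaths may be handled there, but the protocol table would still need to agree.

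**Conclusion.** The point holds as a minor one. Read literally, Rule 1 and the earliest-date note censor at time zero a death that the plan's own definition counts as a primary endpoint event.

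Three conditions must all be met for a patient to be affected: no baseline assessment, death before the cutoff, and no censoring by Rule 7. That is probably very few patients and possibly none. A reader might assume that 0.5% to 1% of 630 patients (about 3 to 6) lack a baseline assessment and conclude that all of them are misclassified. The documents support neither step: they give no such rate, and patients who are alive, or whose deaths Rule 7 censors anyway, lose nothing through Rule 1.

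Power is not at issue, and no direction of bias is claimed. What matters is that the primary endpoint has one definition in the text and another in the table.

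**What to change.** Give Rule 1 the condition that Rule 2 already carries, so that it covers only patients with no baseline assessment and no death. Deaths without documented progression then count under Rule 6 at the date of death, unless Rule 7 applies. The change does not send every such death to Rule 6, and the text should not imply that it does. If the sponsor intends Rule 1 to censor these deaths, the text should state the exception to the PFS definition.

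The wording change is three words, with no new data and no effect on sample size or alpha. Timing matters, however. The SAP addendum, approved 25 August 2017, lists a 90-day safety update with a cutoff of 5 May 2017 after the final PFS analysis, which suggests that the PFS analysis had already been done. Changing the primary rule after lock would be post hoc, and Section 12.2.2 requires an amendment if a principal feature changes. In that case, leave the primary analysis as it is, report how many patients Rule 1 censored and how many of them died, and add a sensitivity analysis counting those deaths as events. The cost is one extra table; if the count is zero, a single sentence is enough.
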